### 7.3.2. Baseline Characteristics

Baseline characteristics (i.e. variables included in the PS-model) will be presented for the evaluable population and appropriate statistical tests will be used for group comparison. P-values, for descriptive purpose only, will be presented.

- For categorical variables:
  - Fisher's exact test will be used for 2\*2 frequency tables (FISHER option in TABLES statement of PROC FREQ)
  - Otherwise, Chi-Square test will be used (CHISQ option in TABLES statement of PROC FREQ)
- For continuous variables, t-test will be used (PROC TTEST), normality assumed considering sample.
- Standardized mean differences (SMDs), variance ratios and weighted density plots for the continuous covariates will be displayed before and after weighting as described in section 7.3.1.2.2.

### 7.3.3. Safety Endpoints with confounding adjustment

[figure not shown]
The primary endpoint analysis with confounding adjustment, (weighted incidence rates) will be conducted using ITT and While On Initial Exposure strategies only for the below safety endpoints:

- Malignancies (excluding non-melanoma skin cancers)
- Mortality
- Opportunistic infections (serious and non-serious)
- Other infections of interest (serious and non-serious)
- Non-melanoma skin cancers (NMSC)
- Serious psychiatric events
- Serious infections

For all endpoints, details about outcome-specific baseline covariates, distributions are displayed in the below table:

Analysis	Endpoints	Dependent variable	Distribution	Baseline covariates
Primary	- Weighted Incidence rate	Number of first event	Poisson	Not adjusted
Primary	- Weighted Event rate	Number of all events	Poisson	Not adjusted

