8.3.2 Analysis of Primary Endpoints

In addition to analyses that consider initial treatment group (BENLYSTA cohort vs. comparison cohort), analyses that specifically account for changes in therapy (in either group) by considering a variety of risk windows will be employed. These analyses will attribute events to BENLYSTA treatment if they occur within the designated risk windows for BENLYSTA exposure and to comparison treatment otherwise. These analyses will allow for a registry patient to contribute person-time to both BENLYSTA treatment, and comparison treatment and as a result, will specifically account for treatment switching to BENLYSTA or from BENLYSTA. Switching between BENLYSTA and comparison treatment will be taken into account in a number of ways in the analysis and will be further defined within the statistical analysis plan. No new analyses for changing between BENLYSTA formulation or stratifying by BENLYSTA formulation are planned. Planned analyses are outlined below; all analyses will be detailed in the statistical analysis plan.

- Analysis by initial treatment group of rate per person years of observation time.
- Analysis by initial treatment group of rate per person years of exposure where BENLYSTA exposure ends 14 weeks (approximately 5 half-lives) after cessation of treatment.
- For serious psychiatric events, BENLYSTA exposure is all time on treatment with BENLYSTA ending 14 weeks (approximately 5 half-lives) after cessation of treatment, with all remaining treatment time attributed to the comparison cohort.
- For serious infections, opportunistic infections and other infections of interest, BENLYSTA exposure is all time on treatment with BENLYSTA ending 6 months after cessation of treatment, with all remaining treatment time attributed to the comparison cohort.
- For NMSC and malignancies excluding NMSC, analysis will be performed where all events will be attributed to BENLYSTA if the patient was ever exposed to BENLYSTA treatment prior to the event and attributed to the comparison cohort otherwise (ie, once exposed, always at risk).
- Mortality will be analyzed applying all the above-mentioned risk windows (eg, 14 weeks, 6 months, and ever-exposed).
- Other risk windows (including risk windows for comparison treatment) may also be assessed and defined in the statistical analysis plan.

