Additional safety analysis will be performed comparing BENLYSTA treatment initiators with patients from the comparison cohort that start or switch an immunosuppressant and that have comparable background medication and treatment history. Subgroup analysis will be performed that will include but not be limited to analysis of patients with positive anti-dsDNA and low complement at baseline, patients with SLEDAI 2000 score at baseline (< 10 vs ≥ 10), SDI (0 vs ≥ 1), steroid use (yes vs no; ≤ 7.5 mg/day vs > 7.5 mg/day), immunosuppressant use (yes vs no; mycophenolate vs immunosuppressant other than mycophenolate), region (US/Canada vs Europe vs other), and race (black race vs other). Safety analyses will be adjusted for potential confounding factors ([Appendix 7](#)) through propensity score methods or other appropriate statistical methods. No new analyses for changing between BENLYSTA formulation or

stratifying by BENLYSTA formulation are planned. Further details of the safety analyses will be described in the statistical analysis plan.

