## **2. SUMMARY OF KEY PROTOCOL INFORMATION**

### **2.1. Changes to the Protocol Defined Reporting Analysis Plan and Previous RAP**

#### **2.1.1. Changes to the Protocol Defined Reporting Analysis Plan**

This RAP provides a more detailed elaboration of the high-level summary of statistical analysis provided in the protocol. There are no changes to the approach originally planned for statistical analysis. However, the following slight modifications have been made:

- Computation of rates (incidence and event) will be done separately for Opportunistic Infections and Other Infections of Interest (these were combined as one in the protocol).

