## 5. CONSIDERATIONS FOR DATA ANALYSES AND DATA HANDLING CONVENTIONS

### 5.1. Study Exposure & Sub-group Display Descriptors

Exposure Group Descriptions			
Study Exposure Group		Data Displays for Reporting	
Code	Description	Description	Order in TLF
A	BENLYSTA	BENLYSTA	2
B	NON-BENLYSTA	NON-BENLYSTA	1

Exposure group comparisons will be displayed using the following specified descriptors:

- BENLYSTA vs NON-BENLYSTA

BENLYSTA group is used for subjects who are exposed to Benlysta while NON-BENLYSTA group is used for subjects who are not exposed to Benlysta. For summary description of baseline characteristics, the exposure group represents subjects' exposure at enrollment (i.e 'Initial Exposure'). For summary of safety and effectiveness endpoints, the exposure group will be defined using the 'Initial Exposure', 'As-Exposed', and/or 'Ever-Exposed' strategies (see Appendix 2, Section 9.2). 'As-Exposed' is defined based on whether or not a subject is using Benlysta at specific period during the study follow-up time; thus a subject's exposure group can change over time depending on switching to or off Benlysta. 'Ever-Exposed' is defined based on whether a subject was exposed to Benlysta at any point in time after enrollment, in this instance a subject's exposure can change only once over time if they were initially 'Unexposed' and then started using Benlysta; once a subject is exposed to Benlysta, they will always be considered as 'Exposed'.

The specific strategy for defining exposure group and the analysis approach for accrued data will be indicated on the TLFs titles and list of the planned data displays provided in Appendix 11 (Section 9.11).

---

 Subjects are considered to have switched from BENLYSTA exposure group if they permanently discontinued Benlysta treatment or missed doses of Benlysta for more than 98 days and do not restart doses of Benlysta on or before day 99 after the last Benlysta medication end date. Subjects are considered to have switched from NON-BENLYSTA exposure group if they initiate or start receiving Benlysta dose anytime during the study follow-up period. Change of different study-qualifying Non-Benlysta Standard of Care (SOC) medications does not count as exposure switching.

Primary analysis will be done on ‘Initial Exposure’ strategy for all endpoints while ‘As--Exposed’ and ‘Ever-Exposed’ will apply for some endpoints as exploratory analysis:

Endpoints	Primary analysis		Exploratory analysis	

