

- Calculation of an individual's subject-years of follow-up for each exposure strategy is shown in Appendix 2 (Section 9.2).

 
Incidence and event rates will be calculated and reported per 100 subject-years. The 95% CI for the rate will be calculated assuming an exact Poisson distribution method [Stokes, 2012].

Model Checking & Diagnostics

• No model-based statistical analysis will be performed; hence there is no model checking and diagnostics to be conducted.

Results Presentation
Total number of events, number and % of subjects with events, total subject-years at-risk, and total subject-years of follow-up will be reported. In addition, incidence proportion (where applicable), incidence rate, event rate and their 95% CI will be presented. The mock-shell tables showing details of data displays are presented in Appendix 12.
Subgroup Analyses
This analysis may be conducted for each study cohort separately (Current Users and Treatment Initiators; Section 5.6.2) . The list of TLF Data Displays is presented in Appendix 11.
Sensitivity Analyses
This analysis will also be conducted using the 'Evaluable Sensitivity' population. Details of the planned displays are provided in Appendix 11: List of TLF Data Displays.

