### 7.3.1.5. Incidence and event rate analysis

Weighted incidence rate per 100 person-years and weighted event rate per 100 person years will be presented for 'ITT' and 'While-On-Initial Exposure' treatment strategies. The 95% CI for the rates will be calculated assuming an exact Poisson distribution method.

Incidence rates will be calculated as total weighted incidence divided by total weighted subject years at risk with corresponding weighted exact Poisson CI:

$$\text{Lower} = \frac{(\text{quantile}('CHISQ', 0.025, 2 * \sum \text{weight} * \text{subject with at least one event})/2)}{\sum \text{weight} * \text{subject years at risk}}$$

$$\text{Upper} = \frac{(\text{quantile}('CHISQ', 0.975, 2 * (\sum \text{weight} * \text{subject with at least one event} + 1))/2)}{\sum \text{weight} * \text{subject years at risk}}$$

Event rates will be calculated as total weighted number of events divided by total weighted follow up time. with corresponding weighted exact Poisson CI:

$$\text{Lower} = \frac{(\text{quantile}('CHISQ', 0.025, 2 * \sum \text{weight} * \text{events}) /2)}{\sum \text{weight} * \text{subject years of follow-up}}$$

$$\text{Upper} = \frac{(\text{quantile}('CHISQ', 0.975, 2 * (\sum \text{events} + 1))/2)}{\sum \text{weight} * \text{subject years of follow-up}}$$

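### The protocol's switching-aware risk-window analyses are reported only as crude rates in the SAP, although the protocol says safety analyses will be adjusted, and the SAP does not declare the change

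*SAP*

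**What the plan says.** **Protocol 8.3.2** lists the planned analyses of the primary endpoints. The first two are by initial treatment group: one over all observation time, one with exposure ending 14 weeks after cessation. Endpoint-specific windows follow:

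- Psychiatric events: 14 weeks after cessation.
- Serious, opportunistic and other infections of interest: "BENLYSTA exposure is all time on treatment with BENLYSTA ending 6 months after cessation of treatment".
- Skin cancer and other malignancies: "all events will be attributed to BENLYSTA if the patient was ever exposed to BENLYSTA treatment prior to the event".
- Mortality: all of these windows.

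The section then states: "Safety analyses will be adjusted for potential confounding factors", by propensity score or other appropriate methods. It makes no exception for the risk windows and leaves details to the SAP.

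**SAP 5.1** makes Initial Exposure primary and says that As-Exposed and Ever-Exposed "will apply for some endpoints as exploratory analysis". SAP 7.3.3 says that the confounding-adjusted analysis "will be conducted using ITT and While On Initial Exposure strategies only for the below safety endpoints". SAP 7.3.1.5 agrees: "Weighted incidence rate per 100 person-years and weighted event rate per 100 person years will be presented for" those same two strategies. AESI rates outside section 7.3 follow 7.1.5.1, which says: "No model-based statistical analysis will be performed; hence there is no model checking and diagnostics to be conducted". SAP 2.1.1 says: "There are no changes to the approach originally planned for statistical analysis". The one modification it lists is the split of opportunistic from other infections of interest.

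**The concern.** In a non-randomised registry, a crude rate contrast mixes any drug effect with differences between the patients who do and do not receive the drug. Protocol section 10 calls this a significant risk.

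SAP 9.2.1.1 concedes that ITT can attribute events to the wrong exposure after a switch, and that While On Initial Exposure drops events after the first switch. For both it refers the reader to As-Exposed. That analysis carries no adjustment, so the analysis offered as the answer to misattribution keeps all the measured baseline confounding that the weighted tables are meant to remove. Someone who has read the protocol and SAP 2.1.1 would not know that the promised adjustment stops at the initial-exposure analyses.

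**Working it through.** **1. Which planned outputs are adjusted (SAP 9.11.2 and 9.11.4)**

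| Strategy | Tables | Adjusted? |
|---|---|---|
| ITT | 24.110 crude, 54.010 weighted | Yes |
| While On Initial Exposure (98 days) | 24.120 crude, 54.020 weighted | Yes |
| As-Exposed, 14 weeks | 24.210–24.212 | No |
| As-Exposed, 6 months | 24.310–24.312 | No |
| Ever-Exposed | 24.410–24.412 | No |

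The position of the word 'only' in 7.3.3 could be read as restricting the endpoints rather than the strategies. Section 7.3.1.5 and the two weighted tables settle it: no weighted output exists for the last three rows.

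**2. How wide the gap is (SAP 9.2.1)**

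- *Malignancy and skin cancer.* Patients on BENLYSTA at enrollment are handled under Ever-Exposed exactly as under ITT. For comparison patients, While On Initial Exposure ends the day before the first BENLYSTA start, which is also where their Ever-Exposed unexposed time ends. What lacks an adjusted counterpart is mainly comparison patients' time after starting BENLYSTA.
- *Infections.* While On Initial Exposure uses 98 days and the protocol window is 6 months (183 days), a difference of 183 − 98 = 85 days per cessation. Time after switching or restarting is also missing from that analysis.
- *Psychiatric events and mortality.* Time after a switch is likewise unadjusted.

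The documents give no switching rates, so the affected person-time cannot be computed.

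**3. The plan's own precision (Protocol Table 8-1)**

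Person-years = N(1 − 0.9⁵)/(−ln 0.9), which gives 7,773.5 for N = 2,000 and 3,886.8 for N = 1,000 (stated: 7,773 and 3,886).

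Half-width = 1.96 × √(r/7,773 + r/3,886) × 100. Serious infection gives 0.927 (stated 0.93), opportunistic infection 0.142 (0.14) and malignancy 0.183 (0.19). The figures reproduce to rounding, except that malignancy would round to 0.18.

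**4. What an unadjusted factor could do (assumed inputs)**

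Take one binary confounder with outcome rate ratio R, prevalence p₁ in BENLYSTA time and p₀ = 30% in comparison time. With no drug effect, the apparent rate ratio is [1 + p₁(R − 1)]/[1 + p₀(R − 1)].

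- Low (R = 1.5, p₁ = 40%): 1.20/1.15 = 1.043
- Middle (R = 2, p₁ = 50%): 1.50/1.30 = 1.154
- High (R = 3, p₁ = 60%): 2.20/1.60 = 1.375

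Multiplying the excess over 1 by the reference rate gives, per 100 patient-years:

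| Endpoint | Reference rate | Low | Middle | High | Stated half-width |
|---|---|---|---|---|---|
| Serious infection | 5.80 | 0.25 | 0.89 | 2.18 | 0.93 |
| Malignancy excl. NMSC | 0.226 | 0.010 | 0.035 | 0.085 | 0.19 |
| Opportunistic infection | 0.136 | 0.006 | 0.021 | 0.051 | 0.14 |

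In the middle case the shift is 96% of the half-width for serious infection, 18% for malignancy and 15% for opportunistic infection.

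**The case against.** The strongest reply is that the commitment has been met. The adjustment sentence names no particular analysis and defers details to the SAP, every AESI gets a weighted ITT and a weighted While On Initial Exposure rate, and the risk-window analyses are labelled exploratory with no formal testing (SAP 2.4, 5.7). Much of this stands. In particular, a reader might infer that no infection or malignancy result is both attributed as the protocol specifies and adjusted. The documents do not support that, because the initial-treatment-group analyses are themselves the first two items in Protocol 8.3.2 and both are weighted.

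The reply does not close the gap. The protocol lists the risk windows as planned analyses of the primary endpoints and makes no exception for them. An exploratory label does not remove confounding from rates set side by side. Separate tables for current users and treatment initiators stratify on one factor only, not on the Appendix 7 list.

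A second reply is that the enrollment propensity score does not describe why patients later start or stop BENLYSTA. That is correct and limits what any simple fix can claim. It is no reason to leave measured baseline differences in place, since adjusting for those needs only baseline data.

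A third is that rich models would fail for rare events. At the reference rates, the 7,773 + 3,886 = 11,659 patient-years give about 26 malignancies and 16 opportunistic infections. A model with score quintiles plus all the key covariates of SAP Table 4 has about 14 parameters, or one to two events per parameter. This stands and shapes the fix.

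**Conclusion.** The gap is real and limited. The SAP leaves the As-Exposed and Ever-Exposed analyses unadjusted, against an unqualified protocol statement, and does not say so in 2.1.1. Adjusted results by initial treatment group exist for every AESI.

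The size of the bias is unknown. Neither document shows an imbalance, so it would go too far to say that the crude risk-window results are confounded by any given amount. Under the assumed range, a true ratio of 1.0 appears as 1.04 to 1.38. For serious infection the shift runs from about a quarter of the stated half-width to more than twice it. For malignancy and opportunistic infection it stays under half of the half-width even in the high case. These comparisons borrow half-widths computed on initial-cohort person-years before crossover. Under As-Exposed, switchers contribute to both groups, so both the precision and the imbalance would differ.

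The change should be made. It does not put the primary adjusted analyses in doubt.

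**What to change.** For each protocol-named endpoint-window pair, in the overall Evaluable population only, add an exploratory Poisson model on person-period records. It should have time-varying exposure, a log person-time offset, the planned enrollment propensity score and subject-clustered robust variance. Report a rate ratio with 95% CI. Clustering is needed because SAP 9.2.1 lets one subject contribute a first event to each exposure group.

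- Use the propensity score alone for rare endpoints. The key covariates of SAP Table 4 may be added for serious infections.
- Keep the crude rates and footnote Tables 24.210 to 24.412 as unadjusted.
- Amend SAP 2.1.1 to state which analyses are adjusted and which are not.

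**Cost.** There are nine pairs: 1 psychiatric + 3 infection + 2 malignancy + 3 mortality. Modelling every cell of Tables 24.210 to 24.412 would instead take (7 + 5 + 3) × 3 = 45 models. The exposure periods and the score are already to be derived, so no new data are needed.

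**Downside to state in the report.** The enrollment score does not model later starting or stopping, so time-varying confounding remains, and estimates for rare events will be imprecise. SAP 7.3.1 stops further propensity-score analysis if balance is not achieved, so the amendment should also say what happens to these models in that case.

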### 7.3.4. Summary

\* Initial exposure: ITT strategy and while on initial treatment.

## 9. APPENDICES

### 9.1. Appendix 1: Schedule of Activities

#### 9.1.1. Protocol Defined Schedule of Events

	Time Points										
	Enrollment  (Day 1)	6 months (±2 months)	12 months (± 2 months)	18 months (± 2 months)	24 months (±2 months)	30 months (±2 months)	36 months (±2 months)	42 months (±2 months)	48 months (± 2 months)	54 months (± 2 months)	60 months (-2/+3 months) 
Data Collection											
Informed Consent	X										
Demographics	X										
Medical History (including SLE History)/General Medical Status	X				X 				X 		
Potential Confounders for Malignancies and/or Infections List	X										
Historical SLE Medications	X										
SLEDAI 2000 	X										
Verify Eligibility Criteria	X										
SLICC/ACR Damage Index	X	X	X	X	X	X	X	X	X	X	X
Record of Current SLE Medications (including corticosteroids) 	X	X	X	X	X	X	X	X	X	X	X
Record of Hospitalizations	X	X	X	X	X	X	X	X	X	X	X
Record of AEs of Special Interest 		X	X	X	X	X	X	X	X	X	X

1. Data collection for enrollment may occur over more than one day.

2. Laboratory values should not be attributed on the SLEDAI 2000 unless laboratory values were obtained within 30 days of the assessment.

3. Only General Medical Status (current status of medical condition and/or medical procedure/surgery since last reported) is collected at 24 and 48 months.

4. SLE Medications include immunosuppressants, biologics, antimalarials, corticosteroids, and investigational agents for SLE. If a subject currently using BENLYSTA changes formulation, the original BENLYSTA record must be updated with a stop date and a new BENLYSTA record needs to be created with a start date for the new formulation. The new BENLYSTA record should also include formulation (IV or SC).

5. AEs of special interest for this study include mortality, serious infections, opportunistic infections and other infections of interest, selected serious psychiatric events, and malignancies (including NMSC). In order to collect additional important information on potential suicidality-related events, should any of the events marked with an asterisk in Appendix 2 of the protocol occur, the investigator will be requested to complete the PSRHQ eCRF (only the first time a serious suicidality-related event is reported) and a PSRQ eCRF (each time a serious suicidality-related event is reported). The PSRHQ and PSRQ are provided in Appendix 3 and Appendix 4 of the protocol, respectively.

6. For the last time point (60 months), data collection is extended by an additional 1 month and therefore can occur up to 63 months after enrollment (Day 1). This is to provide sites with additional time to contact subjects before declaring them as lost-to-follow-up.

7. The data collection time intervals of 6 months  $\pm 2$  months are intended to align with routine standard of care visits for SLE subjects. With the exception of the last time point at 60 months (for which data collection can only be extended up to 63 months), data collection occurring outside the time window ( $\pm 2$  months) should be assigned to the closest time point.

## 9.2. Appendix 2: Exposure Strategy, Analysis Approach and Individual's Subject-Years Calculation

### 9.2.1. Exposure Strategy

For the purpose of statistical analysis, subjects' exposure arm (BENLYSTA vs NON-BENLYSTA) will be assigned using the following exposure strategies: 'Initial Exposure', 'As-Exposed (Time Varying)' with Benlysta risk windows of 14 weeks (98 days) and 6 months, and 'Ever-Exposed'. Hypothetical scenarios for each strategy are represented in Section 9.2.2.

